## 1.0 TRIAL SUMMARY

Abbreviated Title	SRS and Pembrolizumab for Melanoma and Non-Small Cell Lung Cancer (NSCLC) brain metastases (BM).
Trial Phase	Pilot Study
Clinical Indication	Melanoma and NSCLC Brain Metastases
Trial Type	Pilot study with three different radiation dose cohorts.
Type of control	None
Route of administration	Pembrolizumab delivered 200 mg IV every 3 weeks +/- 7 days for at least 2 years, or until progression.
Trial Blinding	N/A
Treatment Groups	All receive pembrolizumab 200 mg IV every 3 weeks +/- 7 days until progression or at least 2 years, with 3 altered radiation dose fractionation groups delivered during first cycle of pembrolizumab.
Number of trial subjects	30 patients.
Estimated enrollment period	2 years
Description of enrollment	
In 2013, we delivered SRS to 20 metastatic melanoma brain metastases patients and 27 NSCLC BM patients. In 2014, we delivered SRS to 14 and 26 patients, respectively. Assuming similar numbers over the next two years, and accruing 45% of patients, we anticipate around 30 patients to enroll.
 
These projected accrual numbers do not reflect the possibility of increased patient referrals from our satellite facilities, and/or increased regional/national referrals, once the trial is opened. We are also not aware of other potentially competing radiation SRS for melanoma and NSCLC brain metastases trials at our institution at this time.

Duration of Intervention	At least 12 months of Pembrolizumab, or until progression.
Duration of Evaluation	3 year ( 2 yrs during accrual, and at least 1 year follow-up for last patient accrued on the study)
Estimated duration of trial	3 years (2 years to accrue + 1 years to follow all patients)
Duration of Participation	3 years
Study Center	Emory University. Atlanta, Georgia.

## 2.0 TRIAL DESIGN/SCHEMA

### 2.1 Trial Overview

Pembrolizumab (i.e. anti-PD-1) and stereotactic radiosurgery (SRS) will be delivered concurrently. The safety and efficacy of this combination is not known. Preclinical data shows promise of this combination, but, has yet to be tested in humans with brain metastases. Pembrolizumab (**200 mg IV every 3 weeks +/- 7 days for at least 2 years, or until progression**) will be delivered on day 1 of cycle 1 and continued until at least 2 years or until disease progression per RECIST 1.1 (see Appendix II for RECIST Criteria). SRS will be delivered on day 2 or day 3 of cycle 1 (i.e. within 24-48 hours after anti-PD-1, with some flexibility allowed for SRS timing during cycle 1).

Three different radiation doses (**Table 1**) will be delivered during cycle 1, in combination with Pembrolizumab. All three radiation doses have different biological effectiveness doses (BED) for acute and late side effects, with Arm C being the most commonly used accepted arm; The **primary objective** will be to assess for dose limiting toxicity (i.e.  **$\geq$  grade 3 CNS toxicity at 3 months**) when different radiation doses (**Table 1**) are delivered; Several secondary objectives will also be evaluated (**section 3.0**); The primary point of the trial (dose limiting toxicity) is  $\geq$  radiation therapy oncology (RTOG) CNS grade 3 toxicity, as defined in the original RTOG 90-05 trial, used to arrive at the currently used safest single radiation dose fraction (**Arm C, Table 1**) schemes for radiosurgery (Shaw E, et al. Int. J. Rad. Onc. & Biol. 2000(47) 291-8); **Grade 3 CNS toxicity is defined as irreversible severe neurological symptoms as outpatient or inpatient requiring medication usage**; It is also possible that while changing the radiation dose levels, we may also find a radiation dose level that is also more immunogenic when combined with PD1 inhibitor; This optimal radiation dose may or may not be the same as that per RTOG 90-05; Preclinical data suggest that dose fraction sizes of 8-10 Gy may be more immunogenic compared with other dose fractionation regimens; This needs to be further evaluated in clinical trials;

All patients will have a baseline PET scan as well as a diagnostic CT chest, abdomen, and pelvis. All pre-treatment and post treatment imaging will be per standard of care for staging and surveillance purposes. They will also have a baseline brain MRI. Post SRS treatment, they will continue to have diagnostic brain MRI (at 6 weeks, and then every 3 months) as well as CT chest/abdomen/pelvis (every 3 months) per standard of care, to evaluate response and to monitor for any unexpected toxicity. Routine standard of care blood work (CBC, BMP, LDH, etc) will also be ordered at baseline and with all subsequent visits.

**Table 1 – Radiation Dose Arms**

Group	Dose per fraction (Gy)	Number of Fractions	Acute BED	Chronic BED
A	6	5	48	90
B	9	3	51.3	108
C. tumor volume < 4cm 	21	1	65.1	168
tumor volume 4-14.15 cm 	18	1	50.4	128

BED = biological equivalent dose. Acute BED is the biological equivalent dose for acute radiation responding tissue, which includes malignant cells. Chronic BED biological is the biologic equivalent dose for late radiation responding tissue, which includes normal brain tissue. Increasing chronic BED doses predicts higher risk of sub-acute and chronic toxicities.

**2.3 Acute Toxicity, Expansion Cohorts, and Late Toxicity Assessment:**

Once 6 patients are enrolled on any given dose level, there will be a waiting period of 3 months (i.e, at time of second post SRS MRI assessment after pembrolizumab dose (i.e, 3 months after Day 1, cycle 1); This time point of 3 months and the dose limiting toxicity (i.e. grade 3 RTOG CNS toxicity) is based on similar timeline used on earlier trial to determine the safest radiation dose. Late toxicity (radionecrosis noted on MRI images will also be analyzed at 6 months and at 1 year, but will not be used to stop enrollment on any given dose arm.);

During this 3 month waiting period, the MRI images and the patients will be assessed for any

signs or symptoms of RTOG CNS toxicity as well as early manifestations of radionecrosis.  $\geq$  Grade 3 CNS toxicity is the only DLT toxicity of principal concern. Patient can still be accrued on other dose arms during this waiting period, while data is being analyzed for safety concerns on a given radiation arm.

- If  $\leq 2/6$  patients develop a DLT on a given radiation arm, accrual on the particular dose arm will continue for another 6 patients for a total of 12 patients per dose arm. RTOG 90-05 used a 20% cutoff at 3 months as the DLT endpoint. We accept 2/6 (33%) based on a biological rationale that if there is slight increase in radiation toxicity, this may be offset by increased systemic responses through immune modulation of radiation when radiation is combined with anti PD-1 (see section 4.0 for biological rationale);
- If  $\geq 3/6$  patients develop a DLT on a given radiation dose arm, this arm will stop accrual and considered unsafe;

[figure not shown]
Late toxicity (i.e, toxicity starting after 3 months) will also be analyzed (a **secondary endpoint of trial**). The principal late toxicity of interest is symptomatic radiation necrosis. This is defined as radiographic (typically on MRI) changes consistent with radiation induced necrosis, and the patient also presenting with increased neurological symptoms. Symptomatic radiation necrosis will be recorded at 6 months and at 12 months;

- The radiation dose arm which meets the lowest DLT (i.e.  $\geq$  Grade 3 CNS Toxicity at 3 months) and late toxicity (any radiation necrosis) endpoints, but also potentially provides higher overall systemic response rate and OS, will be considered the best radiation dose level that can be combined with pembrolizumab.
- Our published series of melanoma patients undergoing SRS alone had an average survival of 38% at 1 yr (Patel KR et al, American J. Clinic. Oncology. 2015, May 16. Epub); Our recent multi-institutional review in collaboration with Duke University suggested 1 yr overall survival of 78% for patients undergoing SRS and PD1 in combination (not published, accepted for annual presentation at American Society of Radiation Oncology Meeting, 2016). Thus, we suspect an improvement of 40% in OS compared with SRS alone. 12 patients on the most immunogenic arm (9Gy x 3), would be expected to have lowest acute and late toxicity, as well as potentially the highest OS benefit. We suspect that this may be the arm for a future trial. However, this has not been tested in any currently prospective manner.

Thus, the total enrollment will be 30 patients, and not less than 18.

## 2.4 Trial Schema

Figure 1: Trial Overview

## 3.0 OBJECTIVES, ENDPOINTS & HYPOTHESES

### 3.1 Primary Objective, Endpoint, & Hypothesis

#### 3.1.1 Primary Objective

- To determine the safety of three different stereotactic radiosurgery (SRS) radiation arms in combination with pembrolizumab for melanoma and non-small cell lung cancer (NSCLC) brain metastasis (BM) patients.

#### 3.1.2 Primary Endpoint

- RTOG grade 3 CNS toxicity at 3 months (the Dose Limiting Toxicity);

#### 3.1.3 Primary Endpoint Definitions

- RTOG grade 3 CNS toxicity is defined as irreversible severe neurological symptoms requiring medications at 3 months;

#### 3.1.4 Primary Hypothesis

- The primary hypothesis of this pilot study is that the use of concomitant SRS using

three different SRS radiation doses with pembrolizumab in melanoma and NSCLC BM patients will be a safe, well-tolerated regimen.

### **3.2 Secondary Objective(s), Endpoint(s) & Hypothesis(es)**

#### **3.2.1 Secondary Objectives**

- b. To evaluate intracranial outcomes – control of the treated lesion in the brain with SRS+ pembrolizumab (i.e. local control), development of additional sites of disease in the brain that were not initially treated with SRS (i.e. anywhere intra-cranial failure), intra-cranial progression free survival (local control of the area that received SRS and anywhere intra-cranial failure), extra-cranial disease response (overall progression free survival), rate of leptomeningeal dissemination, and overall survival.
- c. To determine the overall response rate and overall survival of combination SRS and pembrolizumab compared to:
  - i. SRS alone (historical control)
  - ii. Pembrolizumab alone (historical control)
- d. To evaluate treatment response at un-irradiated and extra-cranial sites (i.e. the abscopal effect) with all three arms;
- e. To compare differences in potential immune biomarkers, pretreatment, during treatment, and post treatment;

#### **3.2.2 Secondary Endpoints**

- a. Time to intracranial outcomes, including local recurrence, anywhere intra-cranial failure, leptomeningeal dissemination.
- b. Overall survival time.
- c. Overall response (intra-cranial and extra-cranial).
- d. Difference in pre and post treatment serum immune biomarkers between the three different radiation arms (see biomarkers section);
- e. Symptomatic radiation necrosis rates at 6 months and at 12 months;

#### **3.2.3 Secondary Endpoint Definitions**

- a. Time to recurrence for each of the intracranial events will be measured from the first treatment on cycle 1, day 1 to the earlier of the recurrence event and/or last follow up/death.
- b. Overall survival will be defined as time from first treatment on cycle 1, day 1 to the earlier of date of death and/or last follow up.
- c. Overall response will be defined using RECIST and immune RECIST Criteria. Response will be measured for all metastatic sites and at un-irradiated sites (i.e. the abscopal effect).
- d. Several serum biomarkers will be analyzed (See section 12) to note any differences between the three arms.

- e. Symptomatic radiation necrosis is defined as evidence of necrosis on MRI images (radiographic evidence or radionecrosis) and a patient having neurological symptoms attributed to the location where the radiosurgery was done (symptomatic); Secondary Hypotheses

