#### **4.2.1 Efficacy of Anti-PD-1, Pembrolizumab, in Melanoma Patients**

Two clinical trials have recently investigated the safety and efficacy of anti-PD-1 pembrolizumab therapy in melanoma. The first published trial by Hamid et al enrolled 135 patients who had never received ipilimumab or had completed ipilimumab greater than 6 weeks

from enrollment. Patients were treated with escalating doses of pembrolizumab, from 2mg/kg q3weeks to 10mg/kg q2weeks. After 4 cycles of induction therapy, patients were continued on pembrolizumab maintenance. The overall response rate was 38% of patients. Response rate was also dose related, with 2mg/kg cohort having a 25% response compared to the 10mg/kg cohort having a 52% response. With a median follow up of 11 months, 81% of patients continued to demonstrate a response and median survival had not been reached, suggesting majority of responses are durable and correlate with survival.

The second reported by Robert et al was a phase I trial of pembrolizumab in metastatic melanoma patients. 173 patients refractory to ipilimumab were randomized in a 1:1 fashion to 2mg/kg q3weeks or 10mg/kg q3weeks. Overall response rate for both dose cohorts was similar: 26%. Of the 41 responding patients, 2 had a complete response (4.9%) while 39 had a partial response (95.1%). Another 24% had stable disease, for a disease control rate of 50%. Progression free survival was 22 weeks for the 2mg/kg arm and 14 weeks for the 10mg/kg arm, with no statistical difference between cohorts. 1 year overall survival was 58% for the 2mg/kg cohort and 63% for the 10mg/kg cohort.

Taken together (**Table 3**), these studies suggest pembrolizumab is an active agent in metastatic melanoma that is well tolerated. Based on these results, the FDA approved pembrolizumab for ipilimumab refractory patients, at a recommended dose of 2mg/kg every 3 weeks +/- 7 days.

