#### **4.2.2 Efficacy of Anti-PD-1, Pembrolizumab, in NSCLC Patients**

Building upon the success of pembrolizumab in melanoma, Garon et al. investigated the safety and efficacy of pembrolizumab alone in 495 stage IV non-small cell lung cancer patients. Overall response rate for entire cohort was 19.4%. Current or prior smokers had a higher response rate than never smoker: 22.5% vs. 10.3%. PD-L1 expression on tumors correlated with higher response, as the 23% of patients with a proportion staining score of 50% or higher had a response of 50%. The role of pembrolizumab in combination with SRS for

NSCLC brain metastases has not been evaluated, and is one of an additional area of investigation in our current trial.

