#### **4.4.1 Safety and Efficacy of Pembrolizumab Alone for Melanoma Brain Metastases**

For both published pembrolizumab trials (Hamid et al & Robert et al), patients with melanoma brain metastases were excluded. With melanoma having a high incidence of developing brain metastases, the efficacy in this population is extremely important. To investigate this further, Kluger et al (Yale group) conducted a phase I study of pembrolizumab alone for melanoma brain metastases. Only patients with asymptomatic lesions and ECOG PS 0-1 were included.

Patients were treated with 10mg/kg q2weeks for 4 total cycles, followed by maintenance therapy. All patients were asymptomatic and not requiring steroids (less than or equal to 10 mg prednisone equivalent is ok)s at the time of start of treatment. 18 patients were enrolled; however 4 (22%) were deemed not evaluable due to intralesional hemorrhage (n=1) and extracerebral progression (n=3). 4 patients (22%) developed a response, with 1 a complete response and 3 with partial responses. Another 3 patients developed stable disease. In the evaluable patients, 7 out of the 14 developed progressive disease (50%). Given the response rate (22%) is similar to the response rate seen in the extra-cranial metastases patients (Hamid et al.; Robert et al.), the authors concluded pembrolizumab does have similar intracranial efficacy.

However in comparison to the standard of care regimens such SRS alone, where 1 year LC rates in prospective studies are 67-75%, the LC rates with pembrolizumab appear significantly lower. With 11 out of the 18 patients (61%) either not completing treatment or developing progressive disease, these tolerability-efficacy rate is markedly lower for pembrolizumab for non-CNS metastases. One possible conclusion is that delayed immunologic response characteristic of pembrolizumab may not be quick enough in the brain, where relatively smaller amounts of progression can quickly increase neurologic morbidity and mortality. Another reason may be that pembrolizumab may not penetrate the blood brain barrier to enough concentrations to make a meaningful clinical impact. Thus, the combination approach of SRS for local control of disease within the brain and pembrolizumab for the control of extra-cranial systemic disease makes the most logical sense. The safety and efficacy of these two combination delivered concurrently is not well characterized.

[figure not shown]

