#### **14.3.2 Response**

Both overall response and response at un-irradiated sites will be determined at week 12, 3 months after completing the first cycle of pembrolizumab and SRS (i.e C1D2-3). Responses will be determined by the RECIST and immune RECIST criteria, as described in APPENDIX II and III. Response will also be assessed at 1 year from C1D2-3. Response rates will be reported along with 95% confidence intervals will be estimated using the Clopper-Pearson method.

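### Sections 3.2.1(d) and 3.2.3(c) define response at un-irradiated sites as the abscopal effect although every patient also receives pembrolizumab, so ordinary drug responses would carry that label

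*Combined protocol and SAP*

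**What the plan says.** Two places in Section 3 equate the endpoint with the abscopal effect, and neither adds a condition:

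- Section 3.2.1(d), objective: "To evaluate treatment response at un-irradiated and extra-cranial sites (i.e. the abscopal effect) with all three arms".
- Section 3.2.3(c), definition: "Response will be measured for all metastatic sites and at un-irradiated sites (i.e. the abscopal effect").

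Section 14.3.2 uses a neutral name: "Both overall response and response at un-irradiated sites will be determined at week 12". It adds a 1-year assessment and reports rates with Clopper-Pearson 95% intervals. It gives no reference rate.

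On treatment, Section 1.0 says "All receive pembrolizumab 200 mg IV every 3 weeks +/- 7 days until progression or at least 2 years". The three arms differ only in radiation. Section 4.4.1 gives the drug the extra-cranial role: SRS is for local control in the brain, and "pembrolizumab for the control of extra-cranial systemic disease makes the most logical sense" completes the rationale for combining them.

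A comparison with historical pembrolizumab alone is planned in Sections 3.2.1(c)(ii) and 3.2.4(c). It is descriptive and concerns overall response. Section 3.2.4(d) then refers to patients who do and do not develop an enhanced abscopal response, in connection with early biomarkers.

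**The concern.** Section 4.6.1 presents the abscopal effect as causal: in the mouse work, irradiating one tumour makes a distant, un-irradiated tumour disappear. The endpoint definition drops the causal part and keeps only the location of the response. In a trial where everyone receives an active systemic drug, location does not identify cause. A patient whose brain metastasis is treated with SRS, and whose lung metastasis then shrinks enough on pembrolizumab to be a RECIST response, meets the definition whether or not radiation contributed.

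Two things are at stake. First, a non-zero rate under this definition could be read as evidence of a radiation effect outside the brain. That reading matters because Sections 2.3 and 14.1.1 justify accepting 2 of 6 patients with a DLT (33%, against 20% in the earlier RTOG trial) partly on the ground that extra toxicity may be offset by systemic responses that radiation promotes. Second, any biomarker contrast made under Section 3.2.4(d) could end up describing ordinary pembrolizumab response under an abscopal name.

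**Working it through.** The protocol states no expected abscopal rate. The check is what rate the definition would produce with no radiation effect outside the brain, using the protocol's own figures.

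**Inputs**

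- Melanoma, drug alone, 135 patients (Section 4.2.1): "The overall response rate was 38% of patients".
- Melanoma, drug alone, 173 ipilimumab-refractory patients (Section 4.2.1): "Overall response rate for both dose cohorts was similar: 26" per cent.
- Melanoma brain metastases, drug alone (Section 4.4.1): 4 responders of 18, stated as 22%.
- NSCLC, drug alone, 495 patients (Section 4.2.2): "Overall response rate for entire cohort was 19.4" per cent.
- Case mix (Section 1.0): melanoma 20 + 14 = 34, NSCLC 27 + 26 = 53, total 87. Melanoma share 34/87 = 39.1%.
- Planned size (Section 14.2): 30 patients (6, 12 and 12).

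**Stated figures.** 4/18 = 22.2%, which agrees with the stated 22%. In the 173-patient trial, 41 responders would be 41/173 = 23.7%, not 26%. The protocol gives no other denominator, and either value leaves the result below inside the same range.

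**Formula.** Background rate = (34 × melanoma rate + 53 × 0.194) / 87, where 53 × 0.194 = 10.282. The chance of at least one responder in an arm of 12 is 1 − (1 − rate)^12.

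| Melanoma rate used | Background rate | Expected of 30 | Expected of 12 | At least one of 12 |
|---|---|---|---|---|
| 22.2% | (7.556 + 10.282)/87 = 20.5% | 6.2 | 2.5 | 94% |
| 26% | (8.840 + 10.282)/87 = 22.0% | 6.6 | 2.6 | 95% |
| 38% | (12.920 + 10.282)/87 = 26.7% | 8.0 | 3.2 | 98% |

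**Sensitivity**

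- The 38% pools several drug doses. Section 4.2.1 gives 25% for the 2 mg/kg cohort of that trial: (8.500 + 10.282)/87 = 21.6%.
- Using 23.7% for the second trial: (8.058 + 10.282)/87 = 21.1%.
- Extremes of case mix: all NSCLC gives 19.4% (5.8 of 30); all melanoma at 38% gives 11.4 of 30.
- Section 5.1.1 admits patients who have progressed on PD-1 therapy. The documents give no response rate for them. At an assumed background of 10%, the expected count is 3 of 30, and the chance of at least one in an arm of 12 is 1 − 0.9^12 = 72%.

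**What the planned interval can show.** For 3 responders of 12, the 95% Clopper-Pearson interval is 5.5% to 57.2%; for 8 of 30 it is 12.3% to 45.9%. Each contains every drug-alone overall rate listed above, so without a reference beside it the interval says nothing about radiation.

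**The case against.** There are several fair points on the plan's side.

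- **The analysis section is already neutral.** A reader might infer that the SAP text commits the trial to reporting an abscopal rate. It does not: Section 14.3.2 never uses the term. The fault lies in two lines of Section 3, echoed in 3.2.4(d). This stands, and it limits the correction needed.
- **A pembrolizumab-alone comparison exists.** It would be wrong to say that none is planned for response. But the one planned is for overall response, which includes the irradiated lesions, and nothing extends it to un-irradiated sites.
- **The term may be shorthand.** Section 4.6.1 also attaches it to control of un-irradiated sites under the combination. That explains the usage, but the same section treats the effect as radiation-induced, so the ambiguity remains.
- **The arms share the drug background.** They do, so a difference between arms could in principle reflect radiation. But enrolment is sequential and non-randomised, and no between-arm test of response is planned. With a 25% background in both 12-patient arms, their counts would differ by 3 or more by chance in 24% of trials.
- **No biomarker responder analysis is specified.** Section 3.2.4(d) is tentative and gives no sorting rule, Section 3.2.2(d) concerns differences between arms, and Section 14.3.5 plans descriptive statistics only. A reader might infer a pre-specified search for abscopal predictors; the documents do not support that. The wording merely invites it.
- **The background rate is borrowed.** The two larger melanoma trials excluded brain metastases, and the 22% is a response in the brain. None of the figures is tied to un-irradiated sites at week 12. This stands, and the size should be given as a range.

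**Conclusion.** The concern holds as a fault of definition and labelling. Sections 3.2.1(d) and 3.2.3(c) name as abscopal any response at an un-irradiated site, in a trial where every patient receives a drug that produces such responses on its own and no arm isolates the drug. This rests on the text and needs no assumption about rates.

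The size is an inference. With no radiation effect outside the brain, roughly 20-27% of patients, about 6-8 of 30, would meet the definition. This assumes that:

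- overall drug-alone response rates stand in for response at un-irradiated sites;
- enrolment follows the 2013-14 radiosurgery case mix;
- every patient has an assessable un-irradiated site (the plan does not say how others enter the denominator); and
- few patients have already progressed on PD-1 therapy.

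If many have, the rate would be lower, but there is no reason to expect zero. A reader might turn this into a firm forecast that one patient in four will be a false abscopal responder. The documents do not support that precision.

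**What to change.** 1. In Sections 3.2.1(d) and 3.2.3(c), delete the parenthesis that names the abscopal effect and call the endpoint *response at un-irradiated sites*, as Section 14.3.2 already does.
2. In Section 3.2.4(d), replace the reference to abscopal response with the same neutral name.
3. In Section 14.3.2, report this rate by histology beside the drug-alone rates already cited, as a descriptive reference, and state that the endpoint alone cannot attribute such responses to radiation.

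A formal rule, such as requiring the lower 95% limit to exceed the reference, is not recommended. Against a reference of 22.0-26.7% it would need 7 of 12 responders in an expanded arm, or 12-14 of 30 overall. The power of the 7-of-12 rule is 16% at a true rate of 40% and 39% at 50%. That is too little for a descriptive secondary endpoint in a pilot.

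The cost is wording in three items of Section 3, plus a reference line and one sentence in Section 14.3.2. No new data, visits or patients are needed. The downside is that the abscopal claim becomes weaker, and the reference is historical and not matched for prior PD-1 exposure, site or time point.
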